Appendix 1: Schedule of Activities (cont.)

Table 1: Induction (cont.)

| Assessment/Procedure | Screening ^a | Induction (28-Day Cycle) up to 2 Cycles | | | | | | | | | | |
|---|------------------------|---|----|----|----|----|----|----|-----|-----|-----|-------------------|
| | Days –14 to –1 | D1 | D2 | D3 | D4 | D5 | D7 | D8 | D15 | D22 | D28 | |
| | | | | | | | | | | | | |
| EORTC QLQ-C30, EQ-5D-5L ^k | | x ^l | | | | | | | | | | |
| HMRA | | | | | | | | | | | | x ^f |
| Bone marrow sampling for HMRA ^m | x | | | | | | | | | | | x ^f |
| Bone marrow sampling ⁿ (MRD/Flow, EDTA, PAXgene [®]) | x | | | | | | | | | | | x ^f |
| Whole blood sampling (flow, EDTA, clinical) | x | x | | | | | | | | | | x ^{f, o} |
| Whole blood sampling PAXgene | | x | | | | | | | | | | |
| RBR sampling/blood serum and plasma (optional) | x | | | | | | | | | | | |
| PK sampling and MIC-1 | | Refer to Appendix 2 | | | | | | | | | | |
| Concomitant medications | x | To be recorded continually; see Section 4.4 | | | | | | | | | | |
| Adverse events | | To be assessed continually; see Section 5.3.1 | | | | | | | | | | |
| Daunorubicin treatment (60 mg/m ² IV) ^p | | x | x | x | | | | | | | | |
| Idasanutlin treatment (PO QD) ^p | | x | x | x | x | x | | | | | | |
| Cytarabine treatment (200 mg/m ² IV) ^p | | x | x | x | x | x | x | | | | | |

AML=acute myeloid leukemia; CT=computed tomography; CTCAE=Common Terminology Criteria for Adverse Events; ECHO=echocardiogram; ECOG=Eastern Cooperative Oncology Group; eCRF=electronic Case Report Form; EDTA=ethylenediaminetetraacetic acid; EOI=end of induction; EORTC=European Organisation for Research and Treatment of Cancer; EORTC QLQ-C30=EORTC Quality-of-Life Questionnaire–Core 30; EQ-5D-5L=EuroQol 5-Dimension, 5-Level; FACIT=Functional Assessment of Chronic Illness Therapy; HMRA=hematologic malignancy response assessment; MRD=minimal residual disease;

Appendix 1: Schedule of Activities (cont.)

Table 1: Induction (cont.)

MUGA=multiple-gated acquisition (scan); PK=pharmacokinetic; PO=orally; PRO=patient-reported outcome; PRO-CTCAE=Patient-Reported Outcomes Common Terminology Criteria for Adverse Events; QD=once a day; RBR=Research Biosample Repository; TB=tuberculosis.

- ^a The screening period starts with the signing of the Informed Consent Form, including the optional Informed Consent Form if appropriate. Results of standard-of-care tests or examinations performed prior to obtaining informed consent and within the defined window may be used as screening and baseline assessments; such tests do not need to be repeated for screening purposes.
- ^b Informed consent must be documented before any study-specific screening procedure is performed.
- ^c Must be performed within 7 days of the planned D1
- ^d If a chest CT is performed up to 28 days prior to study drug administration, a chest X-ray is not required. Patients with a medical history of fungal and TB infections should have a chest CT performed within 28 days prior to study drug administration.
- ^e Vital signs include body temperature, systolic and diastolic blood pressure, pulse rate and respiratory rate. Body surface area will also be measured at screening.
- ^f Should Day 28 not be the last day of the cycle the following will be assessed every 7 days following D28 until end of cycle: biochemistry, hematology, vital signs, ECOG performance status. Bone marrow, HMRA and whole blood sampling should be repeated on the last day of the cycle with D56 as the limit and if not performed within the previous 2 weeks.
- ^g All ECGs should be performed within 2 hours prior to idasanutlin administration and 6 hours after idasanutlin administration.
- ^h Includes systems of primary relevance (e.g., cardiovascular and respiratory systems), systems associated with symptoms (newly emergent or monitored from baseline), and areas associated with tumor assessment (lymph nodes, liver, spleen, and any other areas identified at baseline). Record new or worsened clinically significant abnormalities on the Adverse Event eCRF.
- ⁱ Includes hepatitis B surface antigen, total hepatitis B core antibody, and hepatitis C virus antibody.
- ^j All hematology and biochemistry assessments may be performed up to 3 days prior to the scheduled timepoint. Results must be reviewed by the investigator (or designee) prior to study drug administration.
- ^k PRO questionnaires need to be self-administered before the patient receives any information on disease status and prior to the administration of study treatment. Completion of PROs should occur prior to the performance of non-PRO assessments whenever possible. PRO assessments include the FACIT-Fatigue, EORTC QLQ-C30, EORTC Item Library symptoms, PRO-CTCAE, and EQ-5D-5L.
- ^l Only first cycle of induction.
- ^m At screening, bone marrow examination will require biopsy if an aspirate is not evaluable to confirm the AML diagnosis. For HMRA during study, bone marrow aspirates are required, but bone marrow biopsies may be performed at the discretion of the investigator.

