During the dose-escalation phase, study treatment will be administered as outlined in [Table 1](#). Patients who achieve remission (CR, CRi, CRp, or CRh) after up to 2 induction cycles will receive chemotherapy consolidation treatment up to 4 cycles or allo-HSCT consolidation at the investigator's discretion. Patients who achieved a confirmed remission at the end of chemotherapy consolidation or allo-HSCT or who underwent allo-HSCT in MLFS after induction (see definition of MLFS in [Appendix 19](#)) will receive maintenance treatment for 12 cycles (see [Table 1](#)). In cases where the patient receives allo-HSCT consolidation, maintenance should start within 90 days of the transplant and a full pre-transplant hematologic response assessment must be provided if the transplant is performed more than 4 weeks after end of induction. Patients receiving chemotherapy consolidation should start maintenance right after completion of the consolidation. On the basis of safety, tolerability, and clinical benefit and after consultation with the Medical Monitor, patients may be allowed to continue maintenance at the same dose beyond 12 cycles. All patients will be followed for disease progression and survival. The dose for idasanutlin in consolidation will be determined by the Sponsor upon review of all available safety, PK, pharmacodynamic, and efficacy data. The dose for consolidation will not exceed the dose the patient received during induction.

After the last patient in each cohort has completed the DLT assessment window (first induction cycle), the Sponsor will evaluate the next dose recommended according to the mCRM (see Section [3.1.2.3](#)) and determine doses for the subsequent cohort(s), taking into account relevant demographic, adverse event, laboratory, dose administration, and PK (if available) data. At each dose-escalation step, the dose may be escalated or de-escalated, or an additional cohort at the same dose level may be enrolled.

On the basis of review of real-time safety data from this study and all available data from other studies in the program, dose escalation may be halted or modified by the Sponsor as deemed appropriate.

Although the DLT assessment window is defined as the first induction cycle, cumulative toxicities occurring beyond the first cycle may be considered when determining the MTD for idasanutlin. At the end of the dose-escalation phase, the idasanutlin RP2D in combination with cytarabine and daunorubicin will be decided.

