3.3.5 Rationale for Patient-Reported Outcomes

Symptom presentation in AML is variable with patients frequently presenting with fatigue and loss of appetite at the time of diagnosis. Fatigue is the most common and severe

symptom reported by patients, as well as the most persistent over time (Møller et al. 2012), and is associated with decrements in health-related quality of life (HRQoL) and functioning (Schumacher et al. 2002; Messerer et al. 2008).

In addition to disease-related symptoms, cancer treatments, particularly combination therapies, can produce significant treatment-related symptoms and impacts. Patients with AML in particular experience substantial HRQoL burden during treatment, experiencing the greatest decrements shortly after starting induction and rebounding thereafter (Redaelli et al. 2004; Korol et al. 2017). Research has shown that clinicians may underreport the incidence and severity of symptoms patients experience during treatment (Fromme et al. 2004; Trotti et al. 2007; Pakhomov et al. 2008; Basch et al. 2009; Basch 2010; Quinten et al. 2011; Atkinson et al. 2012). Collecting information about these symptoms directly from patients can provide a better understanding of treatment characteristics and their effects. In order to measure baseline symptoms and characterize symptomatic treatment toxicities from the patient perspective, patients will be asked to report on their experience of relevant treatment-related symptoms selected from the validated PRO-CTCAE item bank. On the basis of preliminary safety data, nausea, vomiting, and diarrhea symptoms were identified as being salient to patients' experience of treatment with idasanutlin.

In this study, important disease- and treatment-related symptoms, as well as functioning will be assessed with the FACIT-Fatigue, EORTC QLQ-C30, and EORTC Item Library (selected symptoms), and PRO-CTCAE. The EQ-5D-5L will be administered for the purpose of producing health utility scores for economic modeling.

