- RFS in patients who achieved remission (CR, CRi, CRp, or CRh), defined as the time from remission (prior to study entry) to the date of hematologic relapse or death from any cause, whichever occurs first
Patients with no RFS event at the time of analysis will be censored at the date of last response assessment.

The following secondary efficacy endpoint will be analyzed in patients enrolled during all phases:

- Change from baseline in patient-reported disease-related symptoms and health-related quality of life at specified timepoints, as assessed through use of the FACIT-Fatigue, EORTC QLQ-C30 (selected scales), and EORTC Item Library (selected symptoms)

EFS, OS, and RFS will be analyzed descriptively using the Kaplan–Meier method (Kaplan and Meier 1958).

Where medians are reached, the corresponding estimated median will be provided, along with the 95% CI by means of the Brookmeyer and Crowley method (Brookmeyer and Crowley 1982). In addition, when available at the time of the analysis, landmark estimates of the proportion of patients who are event free at 6 months, 9 months, 1 year, and 2 years will be provided, along with 95% asymptotic CIs using Greenwood's formula for standard errors.

Descriptive summary statistics and change from baseline will be calculated at each assessment timepoint for the FACIT-Fatigue, EORTC QLQ-C30 scales, and EORTC Item Library symptoms. Further details of the PRO analyses will be provided in the Statistical Analysis Plan.

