Appendix 1: Schedule of Activities

**Appendix 1
Schedule of Activities**

Table 1: Induction

| Assessment/Procedure | Screening ^a | Induction (28-Day Cycle) up to 2 Cycles | | | | | | | | | |
|--|------------------------|---|----|----|----|----|----|----|-----|-----|----------------|
| | Days -14 to -1 | D1 | D2 | D3 | D4 | D5 | D7 | D8 | D15 | D22 | D28 |
| | | | | | | | | | | | |
| Informed consent(s) ^b | x | | | | | | | | | | |
| Serum pregnancy test ^c | x | | | | | | | | | | |
| Demographics, medical history, determination of cytogenetic and molecular risk, physical examination, height, chest X-ray (or chest CT) ^d | x | | | | | | | | | | |
| Vital signs ^e , weight, ECOG performance status | x | x | | | | | | x | x | x | x ^f |
| Triplicate 12-Lead ECG ^g | x | x | x | x | | x | | | | | |
| MUGA or ECHO | x | | | | | | | | | | |
| Coagulation (INR, aPTT [or PTT], and PT) | x | | | | | | | | | | |
| Targeted physical examination ^h | | x | | | | | | x | x | x | x ^f |
| Urinalysis | x | x | | | | | | | | | |
| Hepatitis B and C testing ⁱ | x | | | | | | | | | | |
| C. difficile toxin and toxin-producing C. difficile in stool | x | | | | | | | | | | |
| Chemistry ^j | x | x | x | | | x | | x | x | x | x ^f |
| Hematology ^j | x | x | x | | | x | | x | x | x | x ^f |
| FACIT-Fatigue, EORTC Item Library, PRO-CTCAE ^k | | x | | | | | | | | | |

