Appendix 1: Schedule of Activities (cont.)

Table 2: Chemotherapy Consolidation

| Assessment/Procedure | Consolidation (28-Day Cycle) up to 4 Cycles | | | | | | | | |
|--|---|----|----|----|----|----|-----|-----|------------------|
| | D1 | D2 | D3 | D4 | D5 | D8 | D15 | D22 | D28 |
| Vital Signs ^a , weight, ECOG performance status | x | | | | | x | x | x | x ^b |
| Single 12-Lead ECG ^c | x | x | x | | x | | | | |
| Targeted physical examination ^d | x | | | | | x | x | x | x ^b |
| Urinalysis | x | | | | | | | | |
| Biochemistry ^e | x | x | | | x | x | x | x | x ^b |
| Hematology ^e | x | x | | | x | x | x | x | x ^b |
| FACIT-Fatigue, EORTC Item Library, PRO-CTCAE, EORTC QLQ-C30, EQ-5D-5L ^f | x | | | | | | | | |
| HMRA | | | | | | | | | x ^b |
| Bone marrow sampling for HMRA ^g | | | | | | | | | x ^b |
| Bone marrow sampling for MRD/Flow, EDTA, PAXgene [®] ^h | | | | | | | | | x ^b |
| Whole blood sampling for EDTA and clinical | x | | | | | | | | x ^{b,i} |
| RBR sampling, blood serum and plasma (optional) | x | | | | | | | | |
| PK sampling | Refer to Appendix 2 | | | | | | | | |
| Concomitant medications | To be recorded continually; see Section 4.4 | | | | | | | | |
| Adverse events | To be assessed continually; see Section 5.3.1 | | | | | | | | |
| Cytarabine (1.5 g/m ² IV) ^j | x | x | x | x | x | | | | |
| Idasanutlin (PO QD) ^j | x | x | x | x | x | | | | |

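### QLQ-C30 and EQ-5D-5L are taken in induction only before the first dose, and the next values come at visits that depend on response and transplant route, so no post-induction timepoint is common to all patients

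*Combined protocol and SAP*

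**What the plan says.** Appendix 1, Table 1 has a row for "EORTC QLQ-C30, EQ-5D-5L" with a single mark at Day 1 and none at Days 8, 15, 22 or 28. Footnote l restricts that mark: "Only first cycle of induction". Footnote k sets its timing relative to dosing: "PRO questionnaires need to be self-administered before the patient receives any information on disease status and prior to the administration of study treatment". The row for "FACIT-Fatigue, EORTC Item Library, PRO-CTCAE" is also marked at Day 1 only, but without footnote l, so those three instruments recur at Day 1 of a second cycle.

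Both instruments return at Day 1 of each consolidation cycle (Table 2: "FACIT-Fatigue, EORTC Item Library, PRO-CTCAE, EORTC QLQ-C30, EQ-5D-5L"). In maintenance (Table 3), QLQ-C30 is given at Day 1 of every cycle and EQ-5D-5L every 3 months from Cycle 1. Table 5 schedules all five questionnaires at the discontinuation visit, 28 days after the last dose.

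Section 3.1.2.2 defines who enters consolidation: "Patients who achieve remission (CR, CRi, CRp, or CRh) after up to 2 induction cycles will receive chemotherapy consolidation treatment up to 4 cycles", with allo-HSCT as the alternative at the investigator's discretion. Section 3.1.3 has the same structure for the expansion cohorts.

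For FACIT-Fatigue, QLQ-C30 and the Item Library symptoms, Section 6.3.2 states: "Descriptive summary statistics and change from baseline will be calculated at each assessment timepoint". QLQ-C30 is part of the secondary patient-reported endpoint (Section 2.2.2). EQ-5D-5L serves a separate utility objective (Section 2.5) and is analyzed under Section 6.7. Section 3.3.5 describes patients with AML as "experiencing the greatest decrements shortly after starting induction and rebounding thereafter".

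**The concern.** Induction is where idasanutlin is added to 7+3 and where the primary endpoint is read. It is also where the protocol's own rationale expects quality of life to fall most. QLQ-C30 and EQ-5D-5L contribute nothing from that period except the baseline.

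The later values cannot fully stand in for it, because the visit at which a patient next answers is determined by how induction turned out. A summary by visit then splits patients by response and by consolidation route. A reader of the study report who asks how quality of life and utility stood after induction, across everyone who received it, will find no planned summary that answers.

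**Working it through.** No formula or stated figure is involved. The check traces the two instruments through Appendix 1, Tables 1 to 5, alongside the rules for entering each phase.

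**Values within induction.** Scheduled marks: Cycle 1 Day 1, pre-dose. Cycle 2 Day 1 is removed by footnote l. No other induction day is marked. Scheduled values after the first dose within induction = 0, for one cycle or two.

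**Next scheduled value, by route.**

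| Outcome of induction | Next QLQ-C30 / EQ-5D-5L | Source |
|---|---|---|
| CR, CRi, CRp or CRh, then chemotherapy | Consolidation Cycle 1 Day 1 | Table 2; Sections 3.1.2.2, 3.1.3 |
| Transplant, in remission or in MLFS | Maintenance Cycle 1 Day 1, to start within 90 days of transplant | Table 3; Sections 3.1.2.2, 3.1.3 |
| Treatment failure | Discontinuation visit, 28 days after last dose | Table 5; Section 4.5.6 |

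**Timing.**
- Consolidation Day 1 after one 28-day cycle falls at Day 29, which is 28 days after the first dose. If two cycles both run to the Day 56 limit in footnote f, the gap is 2 × 56 = 112 days.
- For induction failures dosed as scheduled, the discontinuation visit falls between Day 5 + 28 = Day 33 (last idasanutlin) and Day 7 + 28 = Day 35 (last cytarabine) of the last cycle.
- Transplanted patients answer later, at a time set by the transplant date.

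**Who is in each summary.** Consolidation Day 1 holds only remitters on chemotherapy. Maintenance Day 1 holds transplanted patients who start maintenance, including those transplanted in MLFS, together with patients who have completed chemotherapy consolidation. The discontinuation visit holds induction failures together with patients who stop later for other reasons. No row of the schedule holds all induction patients after baseline.

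**Scope.** The dose-escalation cohort (9–15 patients) and the expansion cohorts (40 patients) are affected. The 30-patient post-consolidation cohort has no on-study induction and is not.

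**The case against.** Several points on the other side are sound and limit the claim.

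*Direction of bias.* A reader might infer that change from baseline will be biased toward no loss or an improvement because remitters are compared with a baseline in all patients. The documents do not support this. Change from baseline is ordinarily a within-patient difference, and neither Section 6.3.2 nor Section 6.7 describes a comparison with an all-patient baseline. What stands is that the summary is conditional on remission and route.

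*Share of patients missing.* A reader might subtract the expected CR proportions in Section 6.1 (50–55% high risk, 65–80% favorable/intermediate) from 100% and call 45–50% and 20–35% unmeasured. That does not follow. Consolidation also admits CRi, CRp and CRh, the proportions are for 7+3 alone, and induction failures are scheduled for a post-baseline value at the discontinuation visit.

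*Failures are measured at a similar time.* About Day 33–35 is close to the earliest Consolidation Day 1. This narrows the gap in calendar time. It does not give a common timepoint: the plan summarizes by visit, and transplanted patients fall outside both visits.

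*Contrast with FACIT-Fatigue.* That instrument is also Day 1 only, so a patient with one induction cycle has no post-baseline induction value on any questionnaire. Footnote l removes only Cycle 2 Day 1. The contrast is therefore weak, and deleting the footnote would not close the gap.

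*Descriptive study.* The trial is non-randomized, Section 6.8 calls it hypothesis-generating, and Section 6.3.2 defers PRO details to the Statistical Analysis Plan. No decision depends on these summaries. This sets the weight of the point, but an assessment that was never scheduled cannot be recovered in the analysis plan.

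**Conclusion.** The point holds as a low-cost improvement to the schedule. In the dose-escalation and expansion cohorts, QLQ-C30 and EQ-5D-5L have 0 scheduled values between the first dose and the end of induction. Their next values sit at three kinds of visit, chosen by response and consolidation route. The Consolidation Day 1 change from baseline is conditional on remission and on chemotherapy consolidation, and no post-induction timepoint covers all patients.

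This rests on reading the Appendix 1 marks and footnotes as written, and on change from baseline being computed within patient. It does not establish a biased result, its direction, or a percentage of patients lost. It also does not mean that induction failures lack any post-baseline value. The primary endpoint and the safety analyses are unaffected.

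**What to change.** - Add QLQ-C30 and EQ-5D-5L to Appendix 1, Table 1 at the existing end-of-induction visit: Day 28, or the last day of the cycle if it is extended under footnote f. Give them to all induction patients before the response result is communicated. Because the need for a second cycle is not known at that moment, schedule them at the end of each induction cycle and use the last one as the end-of-induction value.
- Name this visit as the common post-induction timepoint in Section 6.3.2 for QLQ-C30 and in Section 6.7 for EQ-5D-5L.
- Label consolidation and maintenance summaries as conditional on reaching those phases.

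Deleting footnote l alone is not enough, since it adds a value only in patients who receive a second cycle.

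The cost is one extra administration per induction cycle, at an existing visit, of 9 QLQ-C30 items (5 + 2 + 2, Section 4.5.10.2) plus the five EQ-5D-5L items and its visual analogue scale.

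The gain is a post-induction value scheduled regardless of response, in patients still attending. It may not capture the early low point. QLQ-C30 recalls the previous week, so a Day 28 form covers roughly Days 21–28, and EQ-5D-5L asks only about the day itself.

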Appendix 1: Schedule of Activities (cont.)

Table 1: Induction (cont.)

- ⁿ Bone marrow MRD/Flow, EDTA, and PAXgene to be collected at same time as bone marrow for response assessment. If unscheduled bone marrow aspirate is being collected for hematologic response assessment, then bone marrow MRD/flow, EDTA, and PAXgene samples should also be collected. If any MRD assessments are done locally, please record this information in the eCRF. At screening, the priorities for bone marrow samples are EDTA>MRDFlow>PAXgene. At subsequent timepoints the priorities are MRD/Flow>EDTA>PAXgene.
- ^o EDTA only.
- ^p Refer to Section [4.3.2](#) for instructions on study treatment administration.

Appendix 1: Schedule of Activities (cont.)

Table 2: Chemotherapy Consolidation

| Assessment/Procedure | Consolidation (28-Day Cycle) up to 4 Cycles | | | | | | | | |
|--|---|----|----|----|----|----|-----|-----|------------------|
| | D1 | D2 | D3 | D4 | D5 | D8 | D15 | D22 | D28 |
| Vital Signs ^a , weight, ECOG performance status | x | | | | | x | x | x | x ^b |
| Single 12-Lead ECG ^c | x | x | x | | x | | | | |
| Targeted physical examination ^d | x | | | | | x | x | x | x ^b |
| Urinalysis | x | | | | | | | | |
| Biochemistry ^e | x | x | | | x | x | x | x | x ^b |
| Hematology ^e | x | x | | | x | x | x | x | x ^b |
| FACIT-Fatigue, EORTC Item Library, PRO-CTCAE, EORTC QLQ-C30, EQ-5D-5L ^f | x | | | | | | | | |
| HMRA | | | | | | | | | x ^b |
| Bone marrow sampling for HMRA ^g | | | | | | | | | x ^b |
| Bone marrow sampling for MRD/Flow, EDTA, PAXgene [®] ^h | | | | | | | | | x ^b |
| Whole blood sampling for EDTA and clinical | x | | | | | | | | x ^{b,i} |
| RBR sampling, blood serum and plasma (optional) | x | | | | | | | | |
| PK sampling | Refer to Appendix 2 | | | | | | | | |
| Concomitant medications | To be recorded continually; see Section 4.4 | | | | | | | | |
| Adverse events | To be assessed continually; see Section 5.3.1 | | | | | | | | |
| Cytarabine (1.5 g/m ² IV) ^j | x | x | x | x | x | | | | |
| Idasanutlin (PO QD) ^j | x | x | x | x | x | | | | |

